2.7.2.4. Mood

Anxiety and depression are common symptoms in patients with advanced cancer. Integrated geriatric care may alleviate some of these symptoms by providing additional support and reducing social isolation.

PHQ-9 and GAD-7 will be used to measure the prevalence of depression and anxiety in the study population. PHQ-9 and GAD-7 are subscales of the Patient Health Questionnaire, a patient self-rated version of the Primary Care Evaluation of Mental Disorders which is a widely used screening tool for mental health disorders in primary care.(11)

The PHQ-9 is a brief, self-rated questionnaire that was developed to screen for depression. It has 9-items derived from the Diagnostic and Statistical Manual of Mental Disorders, 4th Edition, Text Revision (DSM-IV-TR) criteria for major depressive disorder.(12) For each item the participant is asked to rate how much over the 2 weeks they have been bothered by the symptoms. Scoring is on a Likert-type scale from 0 to 3 (0 indicates not at all; 1 indicates several days; 2 indicates more than half the days; 3 indicates nearly every day). The PHQ-9 scored as a continuous measure has good discriminating power between cases and non-cases of major depressive disorder in cancer outpatients, with an area under the curve (AUC) of 0.94 (95% confidence interval [CI], 0.93-0.95) on ROC analysis.(13)

The GAD-7 is a brief, self-rated questionnaire which was originally developed as a screen for Generalised Anxiety Disorder (GAD), and is frequently used in conjunction with the PHQ-9.(14) Scoring of its 7-item is on a Likert-type scale from 0 to 3 (0 indicates not at all; 1 indicates several days; 2 indicates more than half the days; 3 indicates nearly every day). Anxiety in cancer is thought to be most closely related to the free floating anxiety characteristic of GAD.(15). The GAD-7 is gaining use in screening for a range of anxiety disorders due to its brevity and good psychometric properties.

An estimate of clinically important levels of depression and anxiety can be made using cut-off scores for PHQ-9 and GAD-7. Scores of 5, 10, 15 represent cutpoints for mild, moderate, and severe levels of depression and anxiety, on the PHQ-9 and GAD-7 respectively.(14) A recommended cutpoint for further evaluation and treatment is a score of 10 or more on both measures.(14) A score of 9 or less requires no action or monitoring.

2.7.2.5. Nutrition

The self-MNA will be used to describe the nutritional status in the study population. The MNA is a nutritional screening instrument which was especially developed and validated for use in the elderly.(16) The fully validated self-completed version of the MNA (self-MNA) consists of 6-items which are scored between 0 and 14. (17) The self-MNA takes 3 minutes to complete and is as effective as the full MNA to identify malnutrition.(17) A full MNA score of ≤ 23.5 has been shown in to be a predictor of early death in older adults treated with first-line chemotherapy for cancer.(18) A self-MNA score of ≤ 11 points is considered to be equivalent to a full MNA score of ≤ 23.5 . Standard score interpretation for the self-MNA are: 0-7 = malnourished, 8-11 = at risk of malnutrition, 12-14 = normal nutritional status.

2.7.2.6. Health Utilities

The EQ-5D-5L will be used to describe the health utilities in the study population and as part of the health economic analysis.

2.7.2.7. Chemotherapy Delivery

Chemotherapy delivery will be assessed over the 24 weeks period from start of chemotherapy by dose intensity, dose reduction and treatment delays. Relative dose intensity (RDI) will be calculated based on the ratio of delivered dose intensity of chemotherapy to standard dose for the time period.

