1.2. Study Rationale

1.2.1. Rationale for incorporating comprehensive geriatric assessment in oncology

In oncology, treatment decisions and outcomes are influenced by patient characteristics, disease biology, treatment profile and patient preference for treatment. In older adults, patient characteristics become more important in treatment decisions due to decreased physiological reserves and increased likelihood of comorbidities, functional and psychosocial issues which impact on treatment delivery and tolerance. However, ageing is a highly individual process and older people – even at the same chronological age – have wide variability in their physical, mental and social health status. Therefore, integrating geriatric assessment into routine care of older adults with cancer can help tailor treatment plans to the individual and potentially lead to improved clinical outcomes in terms of quality of life (QoL) and even possibly patient survival.

The prevalence of age-related problems increases sharply after age 70 years, and therefore the International Geriatric Oncology Society has recommended that all cancer patients aged 70 years and older should receive some form of geriatric assessment.(13) The likelihood of age-related problems interacting with treatment is greater also for patients who are planned for treatment with high risk of adverse effects, such as chemotherapy, or for patients with advanced-stage cancer where progression of the cancer can unmask the underlying functional and psychosocial vulnerabilities of the patient.

At the minimum, performing a CGA would result in comprehensive documentation of the individual's physical, functional and psychosocial status at that point in time from which to inform clinical decision-making. A CGA might identify a group of patients who are "fit" who should receive full dose-treatment, a "vulnerable" group of patients who should be subject to some precautions (e.g. chemotherapy dose modification) and a group of patients who are too "frail" for treatment that aims to prolong life who should receive supportive care only.(28) For the vulnerable group of patients, interventions should be tailored to maximise the effective dose and minimise toxicity; this may include modification of treatment regimen and optimisation of their health status to improve chemotherapy tolerance.

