3.7.3.7. Chemotherapy Delivery

Chemotherapy delivery will be assessed over the 24 weeks period from start of chemotherapy by dose intensity, dose reduction and treatment delays. Relative dose intensity (RDI) will be calculated based on the ratio of delivered dose intensity of chemotherapy to standard dose for the time period.

Secondary endpoints of this study are the mean RDI of chemotherapy, the proportion of participants with dose reduction $\geq 10\%$ from previous dose and the proportion of participants with treatment delays of more than 14 days in the two treatment arms at 12 weeks and 24 weeks; they will be compared between treatment arms.

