2.2.1. Inclusion Criteria

1. Aged 70 years or older
2. Pathologically confirmed solid organ cancer or diffuse large B-cell lymphoma
3. Planned for cytotoxic chemotherapy, targeted therapy or immunotherapy
4. Able to effectively understand the language of the quality of life questionnaires in one of the validated languages for the questionnaires
5. Able to give written informed consent before randomisation according to local, national and international regulations

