The remainder of the assessment and development of the management plan must include a personal attendance by the study doctor. This attendance should include performance-based assessment of cognition by Montreal Cognitive Assessment (MoCA). A prioritised list of diagnoses/problems will be developed based on the information derived from the history and examination, and any additional information provided by other means, including an interview of a person other than the patient.

The management plan will be individualised to the patient's needs and may include:

- measures to optimise concurrent health issues
- medication recommendations
- non-medication recommendations (e.g. lifestyle changes, including exercise and diet)
- assessment of the risk of chemotherapy toxicity
- referrals to relevant existing hospital and community services (e.g. allied health services, rehabilitation services, aged care services, palliative care services)

The management plan should be explained and, if necessary, provided in written form to the patient or, where appropriate, their family or carer(s). A written report of the comprehensive geriatric assessment and management plan will be communicated back to the treating oncologist and general practitioner within a maximum of 2 weeks of the assessment via email or mail. More prompt verbal communication may be appropriate.

Participants assigned to the intervention arm will receive a comprehensive geriatric assessment and management within 3 weeks of randomisation. Participants assigned to the intervention arm will continue to see their oncologists who are the participants' primary physician for treatment of their cancer and related health conditions. Further reviews with the study doctor will occur at approximately 12 weeks and 24 weeks after randomisation. The 12 weeks and 24 weeks reviews should include performance-based assessment of functional mobility by TUG. Additional reviews with the study doctor may be scheduled as required depending on medical needs.

Assessments of outcome measures occur at 12 weeks, 18 weeks and 24 weeks following randomisation. After 24 weeks, participants in the intervention arm may continue to receive integrated geriatric care but will not be required to complete further study assessments.

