OARS IADL	7-item, 3-point Likert scale (i) → categorical dichotomous (unimpaired, impaired) (ii) → categorical dichotomous (any decrease in IADL)	1. unimpaired vs impaired 2. decrease in IADL	Baseline Wk12 Wk24	contingency table analysis
Mood				
PHQ9 (depression)	9-item, 4-point Likert scale → categorical ordinal (none, mild, moderate, severe) → categorical dichotomous (not depressed, depressed)	contingency table	Baseline Wk12 Wk24	contingency table analysis
GAD7 (anxiety)	9-item, 4-point Likert scale → categorical ordinal (none, mild, moderate, severe) → categorical dichotomous (not anxious, anxious)	contingency table	Baseline Wk12 Wk24	contingency table analysis
Nutrition				
Self-MNA	6-item questionnaire → categorical dichotomous (malnourished/at risk vs normal) → categorical ordinal (malnourished, at-risk, normal)	1. malnourished/at risk vs normal 2. malnourished vs at-risk vs normal 3. decrease in self-MNA	Baseline Wk12 Wk24	contingency table analysis
Health Utilities				
EQ-5D-5L	5-item, 5-point Likert scale, weighted with Australian utility weights	mean utility weight	Baseline Wk12 Wk18 Wk24	t-test (parametric); or Mann-Whitney test (non-parametric)
QLU-C10D	10-dimensions derived from 13 items of the QLQ-C30, each dimension weighted with Australian utility weights	mean utility weight	Baseline Wk12 Wk18 Wk24	t-test (parametric); or Mann-Whitney test (non-parametric)
Chemotherapy Delivery				
Initial dose (i.e. primary dose reduction)	Categorical dichotomous (full dose, reduced dose)	full dose vs reduced dose	Baseline	contingency table analysis
Mean % dose reduction at outset where applicable	Numerical	mean	Baseline	t-test (parametric); or Mann-Whitney test (non-parametric)
Median % dose reduction at outset where applicable	Numerical	median	Baseline	Mann-Whitney test (non-parametric)
Subsequent dose reduction ≥10%	Categorical dichotomous (yes, no)	yes vs no		contingency table analysis
Subsequent dose escalation	Categorical dichotomous (yes, no)	yes vs no		contingency table analysis
Dose delay >3 days	Categorical dichotomous (yes, no)	yes vs no		contingency table analysis

Early discontinuation	Categorical dichotomous (yes, no)	yes vs no		contingency table analysis
Mean Relative Dose Intensity (RDI)	Numerical	mean		t-test (parametric); or Mann-Whitney test (non-parametric)
Mean cycles delivered	Numerical	mean		t-test (parametric); or Mann-Whitney test (non-parametric)
Median cycles delivered	Numerical	Median		Mann-Whitney test (non-parametric)

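### Chemotherapy-delivery endpoints are clocked from a post-randomisation event, with no rule for patients who never start, so the between-arm comparison can be biased in either direction

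*Combined protocol and SAP*

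**What the plan says.** - **Entry.** SAP 2.2.1 admits patients "Planned for cytotoxic chemotherapy, targeted therapy or immunotherapy". Treatment need not have begun.
- **Intervention.** SAP 2.4.1: "Participants assigned to the intervention arm will receive a comprehensive geriatric assessment and management within 3 weeks of randomisation". Protocol 1.2.1 says an assessment might identify frail patients who "should receive supportive care only", and that benefit may come through its influence on cancer treatment decisions. The endpoint table in protocol 3.7.1 lists dose adjustments due to the assessment under initial dose.
- **Clock.** Protocol 3.7.3.7 and SAP 2.7.2.7 agree: "Chemotherapy delivery will be assessed over the 24 weeks period from start of chemotherapy by dose intensity, dose reduction and treatment delays". RDI is the "ratio of delivered dose intensity of chemotherapy to standard dose for the time period".
- **Initial dose.** SAP Table 4 has two levels, full and reduced. Two further rows are "Mean % dose reduction at outset where applicable" and "Median % dose reduction at outset where applicable".
- **Delay.** SAP 3.5.2 counts a delay from the start of the previous cycle.
- **Status.** In SAP 3.5.2, RDI, later dose reduction and delay are secondary. Primary dose reduction, percentage reduction at outset, early discontinuation and cycles are exploratory, although SAP 2.6.1 also lists initial dose and discontinuation among the secondary measures.
- **Population.** SAP 3.1 states intention-to-treat for eligible and evaluable participants. It does not define evaluable for these endpoints.
- **Data.** SAP 2.5.1 schedules the chemotherapy form at study weeks 12 and 24.

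**The concern.** Starting chemotherapy, the start date and the first dose all come after randomisation, and the intervention is meant to inform all three. If an endpoint exists only for patients who start, or only for those whose dose was reduced, the two arms can be filtered differently before they are compared, and randomisation no longer protects the comparison. Better chemotherapy delivery is a stated secondary hypothesis (SAP 1.3), and secondary tests carry no multiplicity adjustment (SAP 3.4.6). Without a written rule, the denominator could also be settled after it is known who started.

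**Working it through.** **1. The plan's own figures.** The documents give no design figure for chemotherapy delivery. The one sample size, 64 per group for ELFI (SAP 3.2.1: effect size 0.5, two-sided 0.05, 80% power), reproduces: the two-sample t-test needs 63.77, and power at 64 is 80.1%. It is used below only as the number per arm. The study of geriatric consultation cited in protocol 1.1.3 reports regimen changes of 28% higher intensity + 18% lower + 3% delayed = 49%. That equals its stated total, so no share is left for treatment withheld, and the documents give no never-start rate.

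**2. Who has a value under the rules as written.**

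| Endpoint | Rule | Never-starter |
|---|---|---|
| RDI | window opens at first dose | no window |
| Initial dose | full or reduced | no category |
| % reduction at outset | where applicable | no value |
| Delay | from previous cycle | none possible; a late first cycle is not counted either |
| Early discontinuation, cycles | window opens at first dose | no rule |

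SAP 3.1 names dose reduction at outset as something to adjust for. That does not repair the comparison, because this variable can itself be an effect of the intervention.

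**3. RDI, selection alone.** Assumptions, none from the documents: 25% of patients frail; mean RDI 0.90 in the others and r = 0.60 to 0.90 in the frail; SD 0.20; all controls start; a share f = 3% to 20% of the intervention arm, all frail, never starts; no effect on tolerance.

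- Control mean: 0.75 × 0.90 + 0.25 × r
- Intervention starters: [0.75 × 0.90 + (0.25 − f) × r] / (1 − f)

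Central case, r = 0.70 and f = 0.10: control 0.675 + 0.175 = 0.850; starters (0.675 + 0.105)/0.90 = 0.867; difference +0.017. The standard error is 0.20 × √(1/64 + 1/57.6) = 0.036, so the two-sided 5% test rejects 7.4% of the time. Over the whole range the difference is 0 to +0.056 and the rejection rate 5% to 32%.

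Scoring never-starters as 0 over all randomised gives a difference of −f × r: −0.07 in the central case, −0.018 to −0.18 over the range.

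**4. RDI, adding dose changes prompted by the assessment.** RDI is set against standard dose, so a cut lowers it. In the central case, an RDI cut of 0.20 in 0.0167/0.20 = 8.3% of starters cancels the selection shift. At the cited 18% the difference is 0.0167 − 0.036 = −0.019. If 28% also rise by 0.20, it is −0.019 + 0.056 = +0.037.

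**5. Initial dose, full versus reduced.** Let p be the control proportion reduced (assumed 30% to 50%), f the never-start share (5% to 20%, all of whom would have been reduced), and a the share newly reduced because of the assessment. Intervention starters: (p − f + a)/(1 − f). With p = 0.30 and f = 0.10:

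- a = 0: 0.20/0.90 = 22.2%, a difference of −7.8 points
- a = 0.18: 0.38/0.90 = 42.2%, +12.2 points
- break-even: a = f(1 − p) = 7%

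Over the range: −2.6 to −17.5 points at a = 0; +5.0 to +16.3 points at a = 18%; break-even a = 2.5% to 14%.

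**6. Percentage reduction at outset.** Suppose 20 of 100 controls are reduced by 25%, and the intervention arm has the same 20 plus 18 reduced by 15%. Among reduced patients: 25% versus (20 × 25 + 18 × 15)/38 = 20.3%, so the intervention arm looks milder. Over all starters with full dose as 0%: 500/100 = 5.0% versus 770/100 = 7.7%, the opposite order.

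**7. Window.** With a first dose in study week 3, 24 weeks of treatment end at 3 + 24 = week 27. The form is scheduled for week 24, and SAP 3.5.2 reports dose delay at 12 and 24 weeks.

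**The case against.** Several points count on the other side.

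- **Exclusion is not stated.** SAP 3.1 declares intention-to-treat and promises tables of treatment compliance by arm. A reader might infer that the plan drops never-starters. It does not say so; exclusion is only what the definitions produce by default.
- **Steering away may be rare.** The supportive-care sentence in protocol 1.2.1 is background and says only that an assessment might identify such patients. The oncologist remains the primary physician for the cancer (SAP 2.4.1). Chemotherapy may begin before day 8 (protocol 3.6.5.3), while the assessment may take 3 weeks and its report up to 2 more. Where the first dose comes before the assessment, the assessment cannot affect starting. This dilutes the effect but does not remove it.
- **The qualifier is narrow.** It sits only on the mean and median percentage rows, and is undefined. The yes/no initial-dose row does not carry it, and in step 6 that row would show 20% versus 38%, so a reader would see the contradiction.
- **A clock from first dose has a purpose.** It gives equal time on treatment. Counting from randomisation gives a later-starting arm fewer treatment weeks, and scoring never-starters as 0 treats a decision not to treat as the worst delivery. That is a different estimand. This stands, and is why the all-randomised analysis is proposed only as a sensitivity analysis.
- **The window can be covered in part.** Assessments have a ±3-week allowance (protocol 3.6.2), and data may be abstracted from the medical record (protocol 6.7). It is therefore not established that later weeks go unobserved. The mismatch still needs one stated rule.

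**Conclusion.** The point holds in limited form. Delivery endpoints are measured from an event that the intervention can influence, no rule covers patients who never start, and the percentage-reduction rows read as a comparison within a subset formed after randomisation. These comparisons are not fully protected by randomisation.

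A reader might infer that the plan favours the intervention arm. The documents do not support a direction. Losing frail never-starters would help that arm, but dose cuts prompted by the assessment lower its RDI and raise its reduced-dose proportion; steps 4 and 5 show the sign changing within plausible inputs.

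The size is unknown. The figures in steps 3 to 6 illustrate assumed inputs and do not estimate this trial; the central RDI shift is small (+0.017, 7.4% rejection against a nominal 5%). The primary ELFI analysis is unaffected. The change is worth making before analysis because it is cheap and settles the denominator in advance.

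**What to change.** In SAP 2.7.2.7 and Table 4:

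1. Analyse initial dose in all randomised participants as full, reduced or not started. Report by arm the number not starting, the reasons, and the time from randomisation to first dose.
2. Analyse percentage reduction at outset among all who start, with full dose counted as 0%. Remove the where-applicable qualifier from the tested comparison, and give the size of reduction among reduced patients as description only.
3. Label starters-only comparisons of RDI, delay, discontinuation and cycles as conditional on starting. Add an all-randomised sensitivity analysis with never-started counted as 0 for RDI and cycles; it need not be the main comparison.
4. Reconcile the assessment window across SAP 2.5.1, 2.7.2.7 and 3.5.2.

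The cost is SAP wording, an extra category and a few added analyses. The documents show only a schedule row for the chemotherapy form, so first check that start date, dose and reason for not starting are recorded there or can be abstracted from the medical record. The all-randomised figure mixes not starting with tolerance, so it should be shown beside the conditional one. No treatment rule changes.

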2.7.2.8. Healthcare Utilisation

Healthcare utilisation is an important consideration in healthcare service delivery. By improving support to participants, integrated geriatric care may potentially reduce the rate of emergency department visit, unplanned hospital admissions and length of hospital stay. Data on cause and duration of any emergency department visits or hospital admissions during the study period will be extracted from participant's hospital record.

2.7.2.9. Institutionalisation

Social situation and level of care will be used to determine institutionalisation in the study population. Social situation differentiates between living at home alone, home with others or residential care. Level of care is determined by the Aged Care Assessment Service (ACAS) and differentiates between independent, low level care and high level care. For participants who are admitted to hospital, rehabilitation facility or palliative care facility at the time of assessment, the social situation and level of care is considered to be the discharge destination and level of care on discharge, respectively. Institutionalisation is defined in this study as residing in a residential aged care facility.

3. Statistical Procedures

3.1. Overview

All analyses will be conducted as defined in a formal statistical analysis plan (SAP) for the analysis and presentation of data. The SAP will be finalised prior to commencement of study analysis and approved by the Trial Management Committee (TMC).

This document constitutes the formal statistical analysis plan (SAP).

All analyses will be conducted according to the intention-to-treat (ITT) principle: all eligible and evaluable participants will be included in the analysis and analysed according to the arm randomised to (using the as-randomised participant population). By using the ITT principle, the benefits of randomisation are maintained (i.e. that the trial arms are similar except for intervention).

Baseline characteristics by treatment arm will be summarised in frequency tables and by use of descriptive statistics for quantitative variables. Univariate associations will be identified using independent T-test for comparing means, χ^2 or Fisher's exact test for comparing categorical data. Confounder bias will be minimised with logistic regression by adjusting for age plus other relevant differences between the groups (comorbidity, metastatic disease, chemotherapy dose reduction at the outset) in bivariate and multivariate analysis.

Summary tables will be prepared giving numbers of participants by treatment arm and by randomisation irregularities, treatment compliance, eligibility infringements, and losses to follow-up (as per CONSORT guidelines).(19)

Table 1. Baseline characteristics by treatment group

Characteristic	Intervention	Usual Care
Age		
Mean		
Median		
Range		
Sex		
Male		
Female		
Marital status		
Married		
Separated, divorced		
Widowed		
Single		
Household composition		
Lives in the community with spouse, partner or child		
Lives in the community alone		
Lives in residential care		
Cancer site		
Upper gastrointestinal		
Lower gastrointestinal		
Lung		
Urogenital		
Breast		
DLBCL		
Other, not specified		
Cancer stage		
II		
III		
IV		

Treatment intent		
Curative/neoadjuvant/adjuvant		
Palliative		
Initial anti-cancer treatment		
Cytotoxic chemotherapy		
Immunotherapy		
Targeted therapy		
Treatment line		
1 st line		
2 nd line		
3 rd line and beyond		
Patient-reported outcomes		
ELFI score		
EQ-5D-5L utility score		
ECOG 0-1		
KPS \geq 80		
IADL unimpaired		
ECOG 0-1		
KPS \geq 80		
PHQ-9		
GAD-7		

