4.1. Overview

All analyses will be conducted as defined in a formal statistical analysis plan (SAP) for the analysis and presentation of data. The SAP will be finalised prior to commencement of study analysis and approved by the Trial Management Committee (TMC).

All analyses will be conducted according to the intention-to-treat principle: all eligible and evaluable participants will be included in the analysis and analysed according to the arm randomised to (using the as-randomised participant population).

Baseline characteristics by treatment arm will be summarised in frequency tables and by use of descriptive statistics for quantitative variables. Summary tables will be prepared giving numbers of participants by treatment arm and by randomisation irregularities, treatment compliance, eligibility infringements, and losses to follow-up (as per CONSORT guidelines).(67)

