4.2. Sample size requirement

Based on reviews of published studies, a minimal important difference (MID) in patient-reported outcome (PRO) scores has commonly been set at approximately half the standard deviation; that is, equivalent to an effect size of 0.50.(68, 69) An effect size of 0.5 is commonly regarded as a medium difference and a meta-analysis has shown it to be clinically relevant in studies of HRQoL using QLQ-C30 as an outcome measure.(70, 71) The target sample for this study is based on an independent t-test at a 2-sided significance level of 0.05 to have an 80% power to test the null hypothesis of no true between-group difference in the change in the TOI score from baseline to 12 weeks, versus the alternative hypothesis of a difference, with an effect size of 0.5. Under these assumptions, a minimum sample size of 64 evaluable participants in each group (or a total of approximately 128 evaluable participants) who have completed the HRQoL questionnaires at baseline and 12 weeks is required.

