3.2. Sample size

3.2.1. Sample size required

Based on reviews of published studies, a minimal important difference in patient-reported outcome scores has commonly been set at approximately half the standard deviation; that is, equivalent to an effect size of 0.50.(20, 21) An effect size of 0.5 is commonly regarded as a medium difference and a meta-analysis has shown it to be clinically relevant in studies of quality of life using QLQ-C30 as an outcome measure.(22, 23)

The target sample for this study was based on an independent t-test at a 2-sided significance level of 0.05 to have an 80% power to detect a significant between-group difference in ELFI from baseline to 12 weeks with an effect size of 0.5. Under these assumptions, the minimum sample size is 64 evaluable participants in each group (or a total of approximately 128 evaluable participants) who have completed the primary outcome measure at two separate timepoints.

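### The intention-to-treat rule admits only eligible and evaluable participants without defining evaluable for analysis, and the SAP's sample-size criterion no longer requires the week-12 score that the 80% power depends on

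*Combined protocol and SAP*

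**What the plan says.** SAP 3.1 opens with a rule for all analyses. It invokes intention to treat, then states that "all eligible and evaluable participants will be included in the analysis and analysed according to the arm randomised to", and adds in brackets "using the as-randomised participant population". Protocol 4.1 has the same rule: "all eligible and evaluable participants will be included in the analysis". Neither document has a section defining analysis sets.

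*Evaluable* is qualified only where the sample size is set, and the two documents differ. Protocol 4.2 asks for 64 per group, or about 128 in total, "who have completed the HRQoL questionnaires at baseline and 12 weeks is required". SAP 3.2.1 gives the same numbers but asks for participants "who have completed the primary outcome measure at two separate timepoints". Both base the number on "an independent t-test at a 2-sided significance level of 0.05 to have an 80% power", with an effect size of 0.5 on the difference from baseline to 12 weeks.

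**The concern.** A rule cannot be both as-randomised and limited to evaluable participants unless everyone randomised is evaluable. If the sample-size meaning of *evaluable* is carried into the analysis rule, membership of the analysis set depends on what happens after randomisation. Participants who die, become too ill or withdraw before giving a second score would be left out. In an open-label trial whose secondary hypotheses include survival, such losses are related to prognosis and may differ by arm.

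*Eligible* opens a second route. SAP 3.1 plans to tabulate eligibility infringements but does not say whether those participants stay in the analysis.

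The sample-size wording is a separate problem. Someone with baseline and week 18 only, or baseline and week 24 only, satisfies the SAP criterion but contributes nothing to an observed baseline-to-week-12 change. So 128 evaluable participants in the SAP's sense need not mean 128 with the data on which the power was calculated.

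**Working it through.** **Part 1: which participants are in the analysis?** The relevant texts side by side:

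| Place | What it implies |
|---|---|
| Protocol 4.1 and SAP 3.1 | All analyses; intention to treat; as-randomised; but eligible and evaluable only |
| Protocol 4.2 | Evaluable means scores at baseline and week 12 |
| SAP 3.2.1 | Evaluable means the primary measure at any two timepoints |
| Protocol 3.6.5.2 | Enrolment requires a completed baseline, so a second score must come later |
| SAP 2.7.2.1 | Survival time starts at randomisation; people lost to follow-up are censored, not excluded |
| Protocol 3.6.5.6 | Everyone is followed for survival, with no questionnaire condition |
| SAP 3.5.1 | Survival is tested in the palliative-intent subgroup, then the overall study population, then the adjuvant/curative subgroup; no separate analysis set is named |
| SAP 3.4.2.1 | Completion tables count deaths and give percentages of total patients |
| SAP 3.4.3 | The mixed model is relied on for missing scores; no two-score rule |

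The general rule, read with the only available meaning of *evaluable*, excludes anyone with no score after baseline. The endpoint sections point to a wider set. The texts do not settle which prevails. A dropout with one follow-up score stays in under the SAP's two-timepoint reading.

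**Part 2: the sample size.** Inputs from SAP 3.2.1: two-sided alpha 0.05, power 80%, effect size d = 0.5. Allocation is 1:1 (SAP 2.3.1).

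*Reproducing the plan's figure.* The normal approximation is n per arm = 2(1.960 + 0.842)²/d² = 2 × 7.85/0.25 = 62.8, rounded up to 63. The two-sample t-test solution is 63.77, rounded up to 64 per arm and 128 in total. This matches the plan. t-test power at 64 per arm is 80.1%.

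*If some of the 128 lack week-12 data.* The documents give no rate, so the shares are assumptions. With a share s having week-12 data, n per arm = 64 × s. Power comes from the t-test with noncentrality d√(n/2) and 2n − 2 degrees of freedom.

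| Share with week 12 | n per arm | Noncentrality | t-test power |
|---|---|---|---|
| 100% | 64 | 0.5 × √32 = 2.83 | 80.1% |
| 90% | 57.6 | 0.5 × √28.8 = 2.68 | 75.8% |
| 80% | 51.2 | 0.5 × √25.6 = 2.53 | 70.7% |

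*Number to randomise.* To finish with 128 who have both scores, N = 128/(1 − loss). A 10% loss gives 128/0.9 = 142.2, rounded up to 143; a 20% loss gives 128/0.8 = 160. Neither document states an allowance for loss.

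**The case against.** The strongest reply is that *evaluable* was never meant to define the analysis set. The two-timepoint clause is in the sample-size section and nothing links it to SAP 3.1, where the same sentence says as-randomised. The survival sections include everyone, and the joint longitudinal-survival model offered as a sensitivity analysis in SAP 3.4.3.2 would make little sense if early deaths had been removed. Participants with only a baseline score also add little to the arm-by-time estimate.

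Much of this stands, and it rules out three stronger readings that a reader might infer:

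- *The SAP expressly drops early deaths from the survival analysis.* It does not. That requires carrying the sample-size wording into the general rule, and the survival text points the other way. On survival the documents conflict; they do not prescribe exclusion.
- *No second score can exist before week 9 (week 12 less the three-week window), so both survival curves would read about 100% until then.* Protocol 3.6.5.3 schedules a day-7 retest for participants starting chemotherapy on day 8 or later. Protocol 3.6.5.5 offers an assessment at discontinuation. SAP 2.7.1 confirms that the retest index and ELFI are the same measure. Any exclusion would be partial.
- *Recruitment could have stopped early under the looser criterion.* SAP 2.2 describes recruitment in the past tense, and protocol 4.2 keeps the week-12 requirement. No effect on enrolment is shown.

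On power, the figures are for the t-test used to set the sample size. The primary mixed model also uses weeks 18 and 24 and may recover some of the loss.

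What remains is that the rule governing every analysis uses an undefined restriction incompatible with the principle it names. As written, the set could be settled after outcomes are known. The power argument needs no inference about the analysis set.

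**Conclusion.** The point holds as a contradiction to be resolved. The general rule claims intention to treat while allowing randomised participants to be left out. The only meaning on offer for *evaluable* would exclude some early deaths and dropouts, and *eligible* could exclude infringements. How many cannot be sized from the documents, which give no survival, dropout or infringement rates.

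Separately, the SAP's power statement no longer matches its own criterion. The arithmetic behind 64 per arm is right, but 80.1% applies only if all 128 have baseline and week-12 scores. If 10% to 20% lack week 12, power for that contrast is about 76% to 71%. This rests on the assumed shares and on the t-test used for sizing.

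**What to change.** In SAP 3.1, replace the restriction to eligible and evaluable participants with *all randomised participants, by allocated arm*. Then state:

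- overall survival and other event endpoints use all randomised participants;
- the primary mixed model uses all randomised participants with a baseline ELFI, whether or not a later ELFI exists.

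Use *evaluable* only in SAP 3.2.1, restore baseline and 12 weeks as the criterion there, and report power for the number who have both scores.

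The cost is a few sentences of SAP wording. The restated power may be slightly lower than 80%.
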